## 9.4 Statistical analyses

#### Treatment effectiveness:

Descriptive statistics, t-tests, regression and Kaplan-Meier survival analyses will be applied as appropriate to examine treatment effectiveness between drugs, adverse events, drug cost/QALY, and drug survival respectively. Primary treatment effectiveness variables are the mean EASI score, corrected for baseline scores. We will also compare the proportion of patients with an EASI reduction of 50%. For the purposes of analysis, follow up time will be censored in both cohorts if there is switching to another class of therapy and censored in the standard therapy cohort if there is switching to another systemic agent.

The potential effect of *FLG* genotype on treatment response:

In addition to the above analyses, we will conduct a subgroup analysis to investigate whether *FLG* genotype stratifies with treatment response, as *FLG* genotype is potentially an important biomarker but has not been investigated in the context of conventional systemic therapy for atopic eczema. We hypothesise that those with one or more *FLG* loss-of-function mutation(s) respond less well to therapy, as has been seen for the biologic treatment omalizumab [26]. Based on the available literature for patients with moderate-to-severe atopic eczema, we expect 40% of our participants to carry one or more *FLG* loss-of-function mutations. Under these assumptions, all treatment comparisons (AZA vs CsA, AZA vs MTX, CsA vs MTX, dupilumab vs any of the standard systemic medications) are able to detect an effect size as low as 20% difference in treatment responses that are close to the expected MCID\* (=MCID x 80%) with 80% power. Further detail on the differences that can be detected are shown below alongside the expected MCIDs (MCID\*).

The following assumptions are made in these calculations:

- -Available sample sizes are Azathioprine (AZA): 32, Ciclosporin (CsA): 28, Methotrexate (MTX): 20, Dupilumab (Dup): 40 (expecting 40% of our study participants to carry a *FLG* mutation).
- -MCID and corresponding standard deviation is for children and adults combined and reduced by 20% to 5.3.
- -The analysis will use a 2-sample t-test to look at change in score (for the purposes of checking the sample size). The actual analysis will test interactions and therefore have lower statistical power.
- -A 5% significance level (2-sided) will be used.

	EASI score			
Comparison	Difference	Comparison	Difference	MCID*
	detectable with		detectable with	(MCIDx0.8)
	80% power and		80% power and	
	expected sample		expected	
	sizes		sample sizes	
AZA vs CsA	4.4	AZA vs Dup	4.0	5.3
AZA vs MTX	4.8	MTX vs Dup	4.6	5.3
CsA vs MTX	4.9	CsA vs Dup	4.1	5.3

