- b Full blood count, renal and liver function are recommended at all study visits. Other bloods to be done according to local practice (e.g. Hep B, Hep C and HIV). An additional blood sample at week 1 for patients in MTX may be collected according to local practice.
- c After 12 months of participation, questionnaires to be done every 6 months regardless of treatment.
- d For subjects with a diagnosis of asthma of  $\geq$  12 years old.
- e Can be collected at any time during the study.
- f Timepoints are subject to change if decided by the Study Steering Committee.
- g For patients participating in the bioresource, severity assessments (EASI, IGA, POEM, itch severity and A-STAR Bioresource CRF) need to be performed on the same day as the collection of biomaterial.
- h To be conducted as close to the baseline visit/assessments as possible, in particular for participants consenting to the collection of biomaterial for mechanistic studies. For patients only participating in the observational aspects of the study therapy needs to start within a maximum of 28 days following the baseline assessment.

\*\*\* If patient switches their main systemic treatment or restarts the same systemic treatment after a decision for discontinuation by the treating physician has been made (excluding short-term breaks in treatment), Baseline 2 (or if applicable: Baseline 3, 4 etc.) assessments will be performed and then further visits will continue as per original schedule (D1, W4, W16, 6M, etc.).

- i For patients participating in the bioresource, the visit 2 window is +/- 1 week.
- j For patients participating in the bioresource, the visit 3 window is +/- 1 week with +/- 2 weeks in exceptional circumstances.

Participants will be followed up for as long as possible until withdrawal.

While on systemic therapy, follow up is three-monthly after the first 4 weeks up to Visit 6 (12 months). Then follow up will be every six months (for example: Visit 7 will be at 18 months, Visit 8 will be at 24 months and so on).

Once off systemic treatment, patients will be seen every six months.

Patients will be followed up for as long as possible, even if they stop treatment.

The following target visit windows apply: V2 +/-2 weeks (i.e. weeks 2-6), and then +/-4 weeks thereafter (i.e. V3 weeks 12-20 etc.).

EASI - Eczema Area Severity Index
IGA - Investigator Global Assessment
POEM - Patient Oriented Eczema Measure

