#### 3 BACKGROUND AND STUDY OBJECTIVES

## 3.1 Background

The prevalence of atopic eczema (syn. 'atopic dermatitis', 'eczema') has increased 2–3 fold during the last century, affecting up to 20% of children and 4-7% of adults in European countries (1, 2). Severe cases of atopic eczema can have a major impact on health-related QoL of patients and their families. Approximately 85% of cases begin in early childhood and up to 30% of early atopic eczema cases persist into adulthood. Atopic eczema has a strong and clinically relevant association with a range of inflammatory co-morbidities, in particular airway disease (asthma, hay fever), food allergies, atopic eye disease, clinical depression and attention-deficit hyperactivity disorder (3).

Atopic eczema is multifaceted and regulated by a complex array of genetic and environmental factors that lead to epidermal-barrier dysfunction and inappropriate up-regulation in pro-inflammatory immune responses (4, 5). There is increasing recognition that atopic eczema is a highly complex syndrome with multiple causes and mechanistic pathways that clinically can be distinguished by age of onset, severity of illness, ethnic modifiers, response to therapy, and extrinsic flare factors (e.g. infections, stress) (6). The search for objective molecular and laboratory disease severity and prognostic markers is still in its infancy but is essential to inform a personalised therapeutic approach.

Most children and adults with atopic eczema can be treated efficiently with emollients and topical antiinflammatory agents. However, around 5% of patients require systemic immuno-modulatory therapies to induce disease remission and long-term control (7). Ciclosporin (CsA) is currently the only treatment approved in Europe, and only in adults (8). Its long-term use is limited due to the risk of renal toxicity. Alternative systemic immuno-modulatory therapies include methotrexate (MTX) and azathioprine (AZA) (2). Biologic treatments are also being actively researched in early phase trials (e.g. dupilumab and lebrikizumab), and dupilumab has now entered clinical practice, with others expected to enter clinical practice in a couple of years.

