#### **6 STUDY POPULATION**

#### 6.1 Inclusion Criteria

- 1. Paediatric and adult patients with atopic eczema who due to the severity of their disease and/or impact on quality of life are commencing on or switching to another systemic immuno-modulatory agent (e.g. CsA, AZA, MTX or biologic treatments), or who initiated their treatment within the last four weeks and have all required pre-treatment outcomes available.
- 2. Written informed consent for study participation obtained from the patient or parents / legal guardian, with assent as appropriate by the patient, depending on the level of understanding.
- 3. Participants consent to participate in long-term follow up and access to all medical records, including hospital admission records and linkage to data held by NHS bodies or other national providers of healthcare data.
- 4. Diagnosis of atopic eczema in keeping with the UK diagnostic criteria.
- 5. Willingness to comply with all study requirements.
- 6. Competent use of English language, according to patient's age (capable of understanding patient questionnaires).

There is no upper or lower age limit for participation. The decision to start systemic therapy or switch to another systemic agent will be the result of the treating dermatology consultant's decision, following discussion with the patient/parent/legal guardian, without using a pre-specified severity score cut off. It is the treating physician's responsibility to ensure that patients are suitable for the therapy, and that any standard of care treatment or assessments are provided alongside participation in the study as per local requirements.

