#### Baseline 2 (Baseline 3, Baseline 4, etc.) - If switching/restarting systemic treatment

If during participation in the study a patient starts a new systemic immuno-modulatory agent or restarts the same systemic treatment after a decision for discontinuation by the treating physician has been made (excluding short-term breaks in treatment), the patient will have a further 'Baseline' visit and retake all baseline assessments, with exception of family and personal medical history and collection of blood for genetic analyses. Baseline Adverse Events information will also be collected. A new signed Informed Consent will not be required but confirmation of continued consent should be documented in the medical notes. Following this new baseline, visits will be scheduled as per original schedule (Day 1, Week 4, Week 16, and so on). If a patient has simply started on a second systemic agent alongside another, then no baseline visit is required, just 3-monthly visits as per protocol.

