## 7.3 Follow up visits

Follow up visits will occur at 4 weeks after the start of systemic immuno-modulatory therapy, 16 weeks and three-monthly thereafter whilst on systemic therapy up to Visit 6 (12 months). Then follow up visits will be every six months (for example: Visit 7 will be at 18 months, Visit 8 will be at 24 months and so on). Once treatment has been stopped, follow ups are also done six-monthly.

If a patient is recruited within the first 2 weeks after treatment initiation, visit 2 will happen at week 4 (±2 weeks), as per usual schedule of events. In situations when patient recruitment occurs 3-4 weeks after treatment initiation, visit 2 assessments will be conducted on the day of recruitment.

Follow up visit procedures:

a. Confirm informed consent status.

- b. Review of co-morbidities and concomitant medication.
- c. Review of systemic therapy (any changes since last visit/current dose) and disease control (number of controlled weeks).
- d. If treatment has been switched: reasons for switching, and outcomes in patients at the point at which the subsequent treatment is initiated.
- e. Reasons if discontinuing (lack of effectiveness, adverse events, patient preference, disease remission, other).
- f. Smoking and alcohol consumption.
- g. Review of adverse events experienced since the previous visit.
- h. Any A&E, hospital, GP or healthcare skin-related visits, and whether due to disease exacerbations, including skin infection.
- i. Days lost from usual activities due to skin disease (e.g. school, work).
- j. Any further phototherapy (TL01, PUVA or other; number of doses).
- k. Physical exam (at the discretion of the treating physician and with their oversight), including weight, and BP.
- I. Safety blood samples are recommended at all study visits.
- m. EASI, -IGA, POEM, itch severity (NRS), IDQOL/CDLQI/DLQI, EQ-5D-5L (adults)/EQ-5D-Y (4-16 years' old), and RECAP.
- n. Completion of ACT in subjects with diagnosed asthma of ≥ 12 years' old\*.
- o. Optional: collection of blood samples, skin biopsies (≥16 years of age), and skin tape strips for mechanistic work and collection of skin microbiome/metabolite samples, using standardised operation procedures across all study participating centres that have the expertise and facilities to take part on this module.\*\*
- \*ACT only done at 16 weeks and 12 months and then every six months.
- \*\*Only done at 4 and 16 weeks, as well as, one year into treatment.

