## 9.3 Sample size calculation

#### Treatment effectiveness:

Based on the results of the paediatric and adult severe AE treatment surveys we conducted in the UK [24], we expected that at least 200 patients on conventional systemic treatments needed to be recruited within 2 years and followed up for at least 12 months; 40% (80) of patients are expected to be on azathioprine, 35% (70) of ciclosporin, and 24% (50) on methotrexate. This takes a 10% loss to follow up into account. Should the pharmaceutical industry decide to support the A-STAR project financially, then we hope to be able to collect one year follow up data on patients on dupilumab during the life-time of this award.

Under these patient number assumptions, all comparisons of the EASI score (azathioprine vs ciclosporin, azathioprine vs methotrexate, ciclosporin vs methotrexate and dupilumab vs each of the other drugs) are able to detect differences that are below the published minimal clinically important difference (MCID) for each drug with high power (95%) [25]. Differences that can be detected are shown below alongside the MCIDs. Hence, with the projected patient numbers we will be able to detect differences between groups that are clinically meaningful.

	EASI score					
Comparison	Difference detectable with 95% power and expected sample sizes	Comparison	Difference detectable with 95% power and expected sample sizes	MCID		
AZA vs CsA	3.5	AZA vs Dup	3.2	6.6		
AZA vs MTX	3.9	MTX vs Dup	3.7	6.6		
CsA vs MTX	4.0	CsA vs Dup	3.3	6.6		

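### The EASI-50 comparison between drugs carries no baseline adjustment, although baselines may be low because a previous systemic is still working

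*Protocol*

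**What the plan says.** Section 9.4 of the protocol, under treatment effectiveness, names mean EASI as the primary effectiveness variable and corrects it for baseline scores. The next sentence adds a responder analysis: "We will also compare the proportion of patients with an EASI reduction of 50" per cent. It states no baseline correction, covariate or absolute target for that proportion.

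Four other places determine which baselines feed the percentage.

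- **Section 6.1** admits patients who "due to the severity of their disease and/or impact on quality of life are commencing on or switching to another systemic immuno-modulatory agent". The decision is made "without using a pre-specified severity score cut off".
- **Section 7.2** (Baseline 2, 3, 4) says that on an in-study switch, or a restart after discontinuation, "the patient will have a further 'Baseline' visit and retake all baseline assessments".
- **Section 7.3** asks, where treatment has been switched, for "outcomes in patients at the point at which the subsequent treatment is initiated". Its list of reasons for discontinuing covers remission, patient preference and adverse events as well as lack of effectiveness.
- **Section 2**, footnote h of the study schedule, says that for patients in the observational part only, "therapy needs to start within a maximum of 28 days following the baseline assessment". Nothing there or elsewhere says that the earlier systemic has ended before the baseline is scored.

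Section 9.3 gives 6.6 as the MCID for EASI and expects 80 patients on azathioprine, 70 on ciclosporin and 50 on methotrexate.

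**The concern.** EASI-50 is a ratio to baseline, so its meaning depends on what the baseline represents. In a trial with a severity threshold and a common starting condition, the ratio means much the same thing for every patient. This register has neither. A baseline taken in active disease leaves room to halve the score. A baseline taken while the previous drug still controls the skin leaves little room, and for that patient the successful result is no change.

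This would not matter much if every drug had the same mix of baselines. The groups are not randomised, however, and the reason for leaving one drug may influence which drug comes next. Section 3.1 says of ciclosporin, for example: "Its long-term use is limited due to the risk of renal toxicity". A drug often taken up after a switch made for reasons other than failure could collect more controlled baselines than a drug started in flare. The EASI-50 difference would then partly measure who was already controlled.

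**Working it through.** **1. The plan's own figures.** The protocol gives no expected rate, power or sample size for the EASI-50 proportion, so there is none to reproduce. Its EASI figures concern means. The detectable differences in Section 9.3 follow from SD × (1.960 + 1.645) × √(1/n₁ + 1/n₂). With an SD of 5.9, which is back-solved and not stated:

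- azathioprine vs ciclosporin (80, 70): 3.48, stated 3.5
- azathioprine vs methotrexate (80, 50): 3.83, stated 3.9
- ciclosporin vs methotrexate (70, 50): 3.94, stated 4.0

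The exact noncentral t calculation gives 3.50, 3.86 and 3.97, which match to one decimal. The MCID of 6.6 is taken from the same table.

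**2. What a 50% reduction means in points.** Points needed = 0.5 × baseline; the ratio to the MCID is that value divided by 6.6.

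| Baseline EASI | Points needed | Ratio to 6.6 |
|---|---|---|
| 2 | 1.0 | 0.15 |
| 4 | 2.0 | 0.30 |
| 6 | 3.0 | 0.45 |
| 10 | 5.0 | 0.76 |
| 13.2 | 6.6 | 1.00 |
| 20 | 10.0 | 1.52 |
| 30 | 15.0 | 2.27 |

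The two scales agree at 6.6 / 0.5 = 13.2. Below that, a patient can meet EASI-50 with a change smaller than 6.6.

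**3. Three cases under the rule as written.**

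- EASI 4 at baseline and 4 at V3: change 0%, non-responder, although control was kept.
- EASI 6 falling to 3: change 50%, responder, with 3.0 points.
- EASI 0 at baseline: the percentage is undefined.

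**4. Illustration of bias between drugs.** All rates here are assumptions. Two drugs each give 60% EASI-50 in active disease. In one group a fraction f are switchers who start and remain controlled, of whom a fraction q reach EASI-50; the other group has none. Observed rate = 0.60 × (1 − f) + q × f.

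- f = 0.2, q = 0: 0.48 + 0.00 = 48%
- f = 0.2, q = 0.3: 0.48 + 0.06 = 54%

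The chance of a significant result in an unadjusted two-sided 5% test of two proportions, with 80 patients at 60% and 70 at the lower rate:

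- 60% vs 48%: difference 0.12; SE under the null 0.0815, under the alternative 0.0810; (0.12 − 1.96 × 0.0815) / 0.0810 = −0.49, so about 31%
- 60% vs 54%: difference 0.06; both SEs about 0.081; (0.06 − 1.96 × 0.081) / 0.081 = −1.22, so about 11%, and 11.5% (about 12%) counting both tails

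With equally effective drugs this chance should be 5%.

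**The case against.** The strongest reply has four parts.

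**EASI-50 is not misdefined, and refinements belong in the SAP.** A 50% reduction is what EASI-50 means, and a protocol need not give floors or rules for zero baselines. That is accepted. What remains is a comparison that the protocol itself states: in adjacent sentences it corrects the mean for baseline and leaves the proportion bare.

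**The protocol does not say that controlled switchers enter this analysis.** Section 6.1 can be read as requiring that severity or quality-of-life impact drives the switch. Section 7.2 is a visit rule and does not say that each new baseline forms its own analysis unit. Section 9.4 speaks of patients, and it censors follow-up at switching. A reader might infer that every treatment course is counted; the documents do not say so. The censoring rule, however, ends follow-up on the old drug and does not govern the baseline of the new one. Switchers are also eligible at first entry, without a score cut-off. Low on-treatment baselines are thus permitted, but their number is unknown.

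**Noise cannot be quantified.** A reader might treat the SD of 5.9 as measurement error and conclude that 38% of patients with an unchanged true EASI of 4 would count as responders. The documents do not support this. The 5.9 is back-solved from comparisons between patients and probably includes real differences in response. Simulating two visits with no true change, scores floored at 0, gives 38% for a change SD of 5.9, 20% for 3.0, 10% for 2.0 and 0.6% for 1.0. Nor does noise alone bias drugs against each other at a given baseline.

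**Other outcomes show maintained control.** IGA, POEM, well-controlled weeks and drug survival are collected. They help interpretation but do not correct the EASI-50 comparison.

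**Conclusion.** The point stands as a weakness of a supportive analysis. Section 9.4 compares a bare 50% reduction across non-randomised groups whose baselines may have been scored in different treatment states. The arithmetic on single patients follows from the protocol's own MCID. The direction of bias depends on which drug has more low, on-treatment baselines, and its size cannot be derived, because neither the baseline EASI distribution nor the share of controlled switchers is given. The fall to 48-54% and the 12-31% false-positive chance rest wholly on the assumed 60%, 20% and 0-30%.

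Two stronger conclusions should not be drawn. The primary baseline-corrected mean EASI is not affected by this point; EASI-50 is an added analysis and does not appear among the endpoints in Sections 9.1 and 9.2. Nor does it follow that EASI-50 must be limited to baselines of 13.2 or more. Section 9.3 uses 6.6 as a benchmark for differences between groups, not as a threshold for individual response, and such a floor would drop patients whom Section 6.1 deliberately admits for quality-of-life impact.

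**What to change.** Amend the EASI-50 sentence in Section 9.4 as follows.

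1. Compare EASI-50 between drugs with a model adjusted for baseline EASI and for whether the baseline was measured on a previous systemic, or stratify by that indicator. Stratification also shows where one drug has few on-systemic baselines and the adjusted comparison has little overlap.
2. Beside it, report for all patients the proportion at or below a prespecified absolute EASI at V3. The sponsor should choose and justify the value. This outcome recognises maintained control and can classify a baseline of 0, for which EASI-50 is undefined.
3. As a sensitivity analysis only, repeat EASI-50 in patients with a baseline EASI of at least 13.2.

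Cost: a few lines of text and slightly more analysis. Baseline EASI, treatment history and reasons for switching are already collected, so no new data, visits or patients are needed.

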#### Recallability:

Identifiable data will also be used by the central study team to contact patients willing to be invited to take part in further research.

Paper CRFs:  If the online data entry platform is temporarily unavailable, alternative data entry on paper will be possible. Paper CRFs will be used for subsequent data transcription to the eCRF. Paper CRFs can also be used as primary source data collection tool. All identifiable data will be kept separate.
Optional participation in a separate bio-analytic module on biomarkers, mechanistic, genetic and pharmacogenetics studies.
Treatment effectiveness:  - Change in EASI (Eczema Area and Severity Index), EASI-50, EASI-75 and IGA (Investigator's Global Assessment)  - Change in POEM (Patient Oriented Eczema Measure) score  - Change in quality of life (DLQI/CDLQI/IDQOL) (Dermatology/Children's Dermatology Life Quality Index)/EQ-5D)  - Change in ACT (Asthma Control Test) score in patients with a diagnosis of asthma  - Disease control as totally or well-controlled weeks  - Drug survival, and long-term control of disease (e.g. time to discontinuation of treatment).  Pharmacovigilance/safety reporting: All (S)AEs will be captured and MedDRA (Medical Dictionary for Regulatory Activities) coded, including malignancy (melanoma, non-melanoma skin cancer, lymphoma), serious infections (e.g. TB), cardiac and CNS disorders. Relationship to studied drugs and any reason for change in treatment dose and/or change to different treatment will be recorded. We will make use of data linkage to available registers (see above).  Cost-effectiveness analysis:  We will calculate the mean costs and assess generic quality of life with the EQ-5D (which is the health benefit measure preferred by NICE), estimated at different follow up times, for each treatment group/pathway to inform the development of an economic model. This will be in adherence to NICE (2013) methods guidance – whose objective is to estimate (i) long-term cost and QALYs for each treatment options, and (ii) incremental cost-effectiveness estimates to assess the value for money of each intervention. Value of information analysis will be used to identify those areas for further research which have the highest return in terms of population health.  Standardised biorepository of blood, leucocytes and serum for genetic and biomarker analyses as well as skin biopsies (>16 years),

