#### Treatment safety (pharmacovigilance):

Although we will not have adequate statistical power for a comparative analysis of rare and long-term latent adverse events of the different agents within the confines of this three-year project due to the relatively small patient numbers and short follow-up period, we will still be able to conduct a meaningful descriptive analysis of more common adverse events collected over an at least one-year period for each treatment modality.

The initial analyses will consist of comparisons in baseline status between the individuals in the treatment cohorts. For the purposes of analysis (initially) follow-up time will be censored in both cohorts if there is switching to another class of biologic therapy and censored in the standard therapy group if there is switching to a biologic agent. The adverse events of interest are calculated per person time of follow-up, after the start of therapy.

Sample size of the novel biologics/small molecule exposure group will be largely determined by external factors, including:

- 1) NICE technology assessments and resulting recommendations;
- 2) whether NICE indicates the need for pharmacovigilance and recommends patients are registered in our registry;
- 3) funding of by NHS, and
- 4) uptake by prescribing dermatologists.

The size of the comparison cohort will be more under our control. However, it is difficult to anticipate the magnitude of rate differences for adverse events between the cohorts as patients from all groups are likely to have had prior exposure to immunosuppressive drugs.

Assuming i) the risk of adverse event is proportional to the length of exposure with equal risk per year (note this may not be so), ii) power of 80%, and iii) a significance level of 5%, the following applies:

Annual adverse	Rate ratio	Person years exposure
event rate		per group
1/10,000	2	235,508
1/1000	2	23,590
2/1000	2	11,817
1/100	2	2,321
2/100	2	1,146
4/100	2	551
5/100	2	437
10/100	2	201

For guidance, the estimated risk of certain adverse events are as follows:

Squamous cell carcinoma with ciclosporin use 1 in 320 Non-melanoma skin cancer 1 in 1,000 Melanoma in high dose PUVA (phototherapy) 1 in 1,666 Melanoma in normal person 1 in 10,000

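### Section 9.4 censors follow-up at a treatment switch without exempting drug survival, for which Section 2 gives time to discontinuation as the measure

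*Protocol*

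**What the plan says.** Protocol Section 9.4 (Treatment effectiveness) opens by naming descriptive statistics, t-tests and regression, and then says that "Kaplan-Meier survival analyses will be applied as appropriate to examine treatment effectiveness between drugs, adverse events, drug cost/QALY, and drug survival respectively". Four methods are matched in order to four targets, so Kaplan-Meier goes with drug survival.

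Two sentences on EASI follow. The paragraph then sets a general rule: "follow up time will be censored in both cohorts if there is switching to another class of therapy", and follow-up is also "censored in the standard therapy cohort if there is switching to another systemic agent". No analysis is exempted.

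The outcome list in Section 2 includes "Drug survival, and long-term control of disease (e.g. time to discontinuation of treatment" under treatment effectiveness.

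Section 7.3 collects two separate items at follow-up. Item d is "If treatment has been switched: reasons for switching, and outcomes in patients at the point at which the subsequent treatment is initiated". Item e is "Reasons if discontinuing (lack of effectiveness, adverse events, patient preference, disease remission, other".

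Section 9.3 (Treatment safety) has its own, differently worded rule: "follow-up time will be censored in both cohorts if there is switching to another class of biologic therapy".

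Drug survival does not appear in Section 9.1 (primary endpoints) or Section 9.2 (secondary endpoints).

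**The concern.** In a time-to-discontinuation analysis, leaving the index drug for another drug is one of the ways in which the event happens. Kaplan-Meier assumes that a patient censored at time t has the same later risk as those still on the drug at t. A switcher is no longer on the drug, so that assumption fails by construction, whatever the reason for the switch. Censoring switches can only raise the apparent drug survival.

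The rule is also unequal. In the standard therapy cohort a move to any other systemic agent is censored. In the other cohort only a change of class is censored, so a move within a class stays in the analysis. The same behaviour would then give different curves in the two cohorts.

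At stake is any persistence figure that the register publishes, and any comparison of drugs on it. Section 3.3 says that the effectiveness results are to support shared decisions and guidelines.

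**Working it through.** The protocol states no discontinuation rate, switch share, event count or power for drug survival, so there is no figure to reproduce. Every rate below is an assumption, chosen to show a range.

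**Formula.** Let D be the 12-month probability of stopping the index drug for any reason, s the share of stops that are switches, and Λ = −ln(1 − D). Assume constant cause-specific hazards.

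- Switch counted as an event: S = exp(−Λ) = 1 − D.
- Switch censored: S = exp(−(1 − s)Λ) = (1 − D)^(1 − s).

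**Size of the overstatement.**

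| Switch share s | D = 30% (true 0.700) | D = 40% (true 0.600) | D = 50% (true 0.500) |
|---|---|---|---|
| 20% | 0.752 | 0.665 | 0.574 |
| 50% | 0.837 | 0.775 | 0.707 |
| 80% | 0.931 | 0.903 | 0.871 |

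The smallest gap is 0.752 − 0.700 = 0.052 and the largest is 0.871 − 0.500 = 0.371, or about 5 to 37 percentage points. A simulation with 200,000 patients, D = 40% and s = 60% gave 0.814, against 0.815 from the formula.

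**Comparison of two drugs, equal switch shares.** With s = 2/3 for both, 0.70 becomes 0.70^(1/3) = 0.888 and 0.50 becomes 0.50^(1/3) = 0.794. A gap of 20 points reads as about 9. The hazard ratio does not change, because (1 − s) cancels: ln(0.50)/ln(0.70) = 1.94 either way.

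**Comparison of two drugs, unequal switch shares.** Drug A: D = 50%, 70% of stops by switch. Drug B: D = 30%, 30% by switch.

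- True hazard ratio A/B: 0.693/0.357 = 1.94, with survival of 0.50 against 0.70.
- Switches censored: (0.693 × 0.3)/(0.357 × 0.7) = 0.208/0.250 = 0.83, with survival of 0.812 against 0.779.

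The drug with the worse persistence now looks better.

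**Unequal rule between cohorts.** Give both cohorts the same true behaviour: D = 40% (Λ = 0.511) and s = 60%. Suppose that half of the switches in the non-standard cohort are within class, so that they are not censored and count as events.

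- Standard: exp(−0.511 × 0.4) = 0.815.
- Other cohort: exp(−0.511 × (0.4 + 0.6 × 0.5)) = exp(−0.511 × 0.7) = 0.699.
- Apparent hazard ratio: 0.7/0.4 = 1.75, where the truth is 1.00.

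As the within-class share goes from 0 to 1, this ratio goes from 1.0 to 2.5.

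**Mix of reasons.** With 60% of stops being switches (censored) and 20% being remission, remission makes up 0.2/(1 − 0.6) = 50% of the events left in the curve, against 20% of all stops. This is a reason to show remission separately.

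**The case against.** The strongest reply is that the censoring sentence was never meant for drug survival. It comes after two sentences on EASI, and the safety rule in Section 9.3 is worded in nearly the same way, so it may be a general device for attributing follow-up to the drug in use. That reading is possible. However, the paragraph does not say so, and drug survival is the only time-to-event analysis that it names. Section 9.3 carries a separate rule for safety, which leaves this one to govern effectiveness, where Section 2 places drug survival.

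A second reply is that a stop dated before the new drug starts would already be an event, so switches need not be lost. That may hold for some patients. The text does not say which date governs, and Section 7.3 records switching and discontinuing as separate items, so an analyst could take only the latter as the event.

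A third is that an SAP may define the event. Omitting the definition from a protocol would indeed be no fault. Here, though, the protocol states a rule, and an SAP that counted switches as events would depart from its wording.

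Three limits stand. The figures above are illustrations on assumed rates. With equal switch shares the hazard ratio is unaffected, so reversed rankings need unequal shares. And drug survival lies outside Sections 9.1 and 9.2.

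**Conclusion.** The point holds as a conflict within the protocol: Section 9.4, read literally, censors part of what Section 2 sets out to measure, and does so by a different rule in each cohort. The direction is certain wherever switches are censored: persistence is overstated. The size is not known. Under constant hazards, with 12-month persistence of 50% to 70% and 20% to 80% of stops being switches, it is about 5 to 37 percentage points. It should be fixed before any drug-survival result is produced, but it leaves the primary EASI endpoint alone.

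A reader might infer three stronger things that the protocol does not support:

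- That switching is the main form of discontinuation. No section gives the share of stops that are switches.
- That stopping for remission is counted as failure of long-term control. Section 2 offers time to discontinuation only as an example, and Section 7.3 records remission as a reason of its own. The fair statement is that the outcome as described does not separate the two.
- That drug survival is the register's main long-term effectiveness measure. It is one named outcome in Section 2. The endpoints to 12 months in Section 9.2 are EASI, POEM, IGA and quality of life.

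**What to change.** Reconcile Sections 2 and 9.4 as follows.

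- State that the switch-censoring rule in Section 9.4 does not apply to drug survival.
- Define the event as stopping, or switching away from, the index drug, with the same definition in both cohorts.
- Do not count short-term breaks or the addition of a second systemic agent as events, in line with the notes to the study schedule and the text on repeat baselines in Section 7.2.
- Censor at last visit, withdrawal, or entry to a blinded trial. Section 7.6 already provides for the last of these.
- As a supplement, report cumulative incidence by the reasons recorded under Section 7.3, with remission shown separately and death as a competing event.

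The cost is wording only. A switch already triggers a new baseline visit, and the reasons for switching and stopping are already collected. The downside is that reported persistence will be lower than under the present rule.
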